#### 3. Semitandem Stand

Instructions: Now I want you to try to stand with the **side of the heel of one foot touching the big toe of the other foot for about 10 seconds**. You may put either foot in front, whichever is more comfortable for you.

Please watch while I demonstrate. Grading: Stand next to the participant to help him or her into semitandem position. Allow participant to hold onto your arms to get balance. Begin timing when participant has the feet in position and let's go.

- 2 = Held for 10 sec
- 1 = Held for less than 10 sec; (number of seconds held: \_\_\_\_\_sec)
- 0 = Not attempted

#### 4. Side-by-Side stand

Instructions: I want you to try to **stand with your feet together, side by side, for about 10 sec**. Please watch while I demonstrate. You may use your arms, bend your knees, or move your body to maintain your balance, but try not to move your feet. Try to hold this position until I tell you to stop. Grading: Stand next to the participant to help him or her into the side-by-side position. Allow participant to hold onto your arms to get balance. Begin timing when participant has feet together and let's go.

- 2 = Held of 10 sec
- 1 = Held for less than 10 sec; (number of seconds held: \_\_\_\_\_ sec)
- 0 = Not attempted

### 5. Tandem Stand

Instructions: Now I want you to try to stand with the heel of one foot in front of and touching the toes of the other foot for 10 sec. You may put either foot in front, whichever is more comfortable for you. Please watch while I demonstrate.

Grading: Stand next to the participant to help him or her into the side-by-side position. Allow participant to hold onto your arms to get balance. Begin timing when participant has feet together and let's go.

- 2 = Held of 10 sec
- 1 = Held for less than 10 sec; (number of seconds held: \_\_\_\_\_ sec)
- 0 = Not attempted

Balance Ordinal Score:

- 0 = side by side 0-9 sec or unable
- 1 = side by side 10, <10 sec semitandem
- 2 = semitandem 10 sec, tandem 0-2 sec
- 3 = semitandem 10 sec, tandem 3-9 sec
- 4 = tandem 10 sec

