#### 2. Balance Testing

Begin with a **semitandem stand** (heel of one foot placed by the big toe of the other foot). Individuals unable to hold this position should try the side-by-side position. Those able to stand in the semitandem position should be tested in the full tandem position. Once you have completed time measures, complete ordinal scoring.

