#### 3. Tandem Stand

Instructions: Now I want you to try to **stand with the heel of one foot in front of and touching the toes of the other foot for 10 sec**. You may put either foot in front, whichever is more comfortable for you. Please watch while I demonstrate.

Grading: Stand next to the participant to help him or her into the side-by-side position. Allow participant to hold onto your arms to get balance. Begin timing when participant has feet together and let's go.

- 2 = Held of 10 sec
- 1 = Held for less than 10 sec; (number of seconds held: \_\_\_\_\_ sec)
- 0 = Not attempted

Balance Ordinal Score:

• 0 = side by side 0-9 sec or unable

- 1 = side by side 10, <10 sec semitandem
- 2 = semitandem 10 sec, tandem 0-2 sec
- 3 = semitandem 10 sec, tandem 3-9 sec
- 4 = tandem 10 sec

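### The SPPB Tandem Stand grading line describes the side-by-side stance and contradicts the rest of its own item, so an assessor who follows that line could overscore balance by up to 2 of 12 points

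*Protocol*

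**What the plan says.** The protocol names the SPPB as the physical-performance measure among the secondary endpoints (Section 6.2) and schedules it at R, T1, T2 and T3 (Section 7, Table 5). Section 7 says the scales are attached as an appendix, so the appendix form is operating text.

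The balance part begins with the semitandem stance and then branches. For those who fail it: "Individuals unable to hold this position should try the side-by-side position". For those who pass: "Those able to stand in the semitandem position should be tested in the full tandem position".

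Under Tandem Stand the participant is asked to "stand with the heel of one foot in front of and touching the toes of the other foot for 10 sec". The grading line for the assessor in the same item reads "Stand next to the participant to help him or her into the side-by-side position", followed by "Begin timing when participant has feet together and let's go".

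The Balance Ordinal Score printed below uses tandem seconds. A score of 2 is tandem 0-2 s, the next level is "3 = semitandem 10 sec, tandem 3-9 sec", and 4 is tandem 10 s.

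**The concern.** The two halves of one test item describe different stances. The participant hears heel-to-toe, while the person holding the stopwatch is told to set up and time feet together. On the form's own branching, side-by-side is the easier stance, because it is the fallback for those who cannot hold semitandem. A time taken side-by-side and entered as a tandem time can therefore only flatter the score.

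What is at stake is a secondary endpoint. Section 9 analyses change over time by repeated measures ANOVA and by linear regression on the difference between baseline and follow-up. If every assessor followed the grading line, the upper levels of the balance item would merge and improvement there could not be seen. If some followed it and others did not, a participant's balance score could move between visits with no change in function. Section 8.1 places the recruitment assessment around discharge and Section 8.2 allows T1 at home or in hospital, so a change of assessor is possible. The protocol does not say whether it happens.

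**Working it through.** The plan states no figure to reproduce. The check compares the texts and then enumerates the form's own scoring.

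**Step 1: the three stance items.**
- Semitandem: the grading line names its own stance, "Stand next to the participant to help him or her into semitandem position", and starts timing when the feet are in position.
- Side-by-side: the grading line names side-by-side and starts timing with the feet together.
- Tandem: the grading line is word for word the side-by-side one.

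The pattern suggests a copying slip. The same text stands under Tandem Stand on all four visit forms (item 5 at R, item 3 at T1, T2 and T3). Nothing elsewhere in the protocol corrects it.

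**Step 2: who reaches the item.** Only participants who hold semitandem are tested in tandem. Those who do not hold it for 10 s score 0 or 1 whichever stance is used later, so they are unaffected.

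**Step 3: score under each reading.** Inputs are the Balance Ordinal Score and the SPPB summary range of 0 to 12. Assumption: a participant who has just held semitandem for 10 s also holds side-by-side for 10 s. The protocol does not state this, but it fits the form's order of difficulty. Following the grading line then always records a tandem time of 10 s, which scores 4.

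| Semitandem | True heel-to-toe time | Score, heel-to-toe | Score, grading line | Difference |
|---|---|---|---|---|
| 10 s | 0-2 s | 2 | 4 | 4 - 2 = +2 |
| 10 s | 3-9 s | 3 | 4 | 4 - 3 = +1 |
| 10 s | 10 s | 4 | 4 | 0 |
| under 10 s | not tested | 0 or 1 | 0 or 1 | 0 |

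The largest error is 2 of 12 points, and levels 2, 3 and 4 collapse into 4.

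**Step 4: timed bands on the same form.**
- Chair stands: the bands are below 11.1, 11.2-13.6, 13.7-16.6 and above 16.7 s. Readings of exactly 11.1 s and 16.7 s have no score. Without a rounding rule, readings such as 11.15, 13.65 or 16.65 s have none either.
- Gait over 2.44 m: score 1 is above 5.7 s and score 2 is 4.1-6.5 s, so times above 5.7 s and up to 6.5 s fit both, an overlap of 6.5 - 5.7 = 0.8 s. The speed at 6.5 s is 2.44 / 6.5 = 0.375 m/s, outside the 0.44-0.60 m/s printed beside score 2. A reading of exactly 3.1 s falls between scores 3 and 4.

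**The case against.** The best defence is that the item as a whole says tandem. The branching rule, the item title, the instruction read aloud, the demonstration and the score labels all point to heel-to-toe. To inflate the score, an assessor would have to demonstrate heel-to-toe, place the participant side-by-side, and still write the result down as tandem seconds. A trained assessor may well notice the slip. This stands: the error is conditional on one line overriding the rest of its item.

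The second defence is that the appendix shown is in English. Section 7 says all scales used are validated in Italian, Norwegian and Romanian, and those forms are not shown. Whether they carry the slip is unknown, so scoring error at the sites cannot be asserted. This also stands. It does not excuse the wrong text here, and it is a reason to check the national forms.

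A reader might go further and infer that balance scores in this trial will be inflated, that the sites will differ systematically, or that the treatment comparison is biased. The documents support none of these. They do not show which line assessors follow, they give no distribution of tandem times from which a mean error could be computed, and the form does not differ by arm. Applied uniformly, the line would compress change rather than favour one group.

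**Conclusion.** The contradiction is real and repeated on all four visit forms. Its consequence is conditional. An assessor who follows the grading line would record 4 for participants whose true balance score is 2 or 3, an error of +2 or +1 on the 0-12 total, provided they also hold side-by-side for 10 s. An assessor who follows the participant instruction would make no error. The possible effect is a ceiling in the balance item or variation between assessors. Its average size cannot be estimated from the protocol.

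The 30-day rehospitalization endpoint and the sample size are not affected. The point is worth correcting because the form is operating text for a named secondary endpoint and a time taken in the wrong stance cannot be converted afterwards. The band defects are minor: the chair-stand gaps concern isolated readings, and the gait overlap is the wider of the two.

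**What to change.** On the R, T1, T2 and T3 forms, replace the grading line under Tandem Stand with, for example: stand beside the participant, help him or her into the tandem (heel-to-toe) position, and begin timing once the feet are in that position. Leave the participant instruction and the Balance Ordinal Score as they are. Check that the Italian, Norwegian and Romanian forms say the same, and use one corrected form at every visit. If any form with the old line is already in use, ask the assessors which stance they timed.

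In the same edit, make the timed bands contiguous and non-overlapping:
- State a rounding rule (0.1 s).
- Assign chair-stand times of 11.1 s and 16.7 s to a band. With the middle bands unchanged, the only adjoining ones are scores 4 and 1 respectively.
- Reconcile the gait limits for scores 1 and 2 with the speeds printed beside them, and place the 3.1 s reading.

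The cost is one sentence in four places, a few band limits, and a comparison with the national forms. No assessment is added.

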#### 6. 8' Walk (2.44 meters)

Instructions: This is our walking course. If you use a cane or other walking aid when walking outside your home, please use it for this test. I want you to walk at your usual pace to the other end of this course (a distance of 8'). Walk all the way past the other end of the tape before you stop. I will walk with you. Are you ready? Grading: Press the start button to start the stopwatch as the participant begins walking. **Measure the time** take to walk 8'. Then complete ordinal scoring.

Time: sec

Gait Ordinal Score:

- 0 = could not do
- 1 = >5.7 sec (<0.43 m/sec)

- 2 = 4.1-6.5 sec (0.44-0.60
- m/sec)
- 3 = 3.2-4.0 (0.61-0.77 m/sec)
- 4 = <3.1 sec (>0.78 m/sec)

**Summary Ordinal Score**: Range: 0 (worst performance) to 12 (best performance). Shown to have predictive validity showing a gradient of risk for mortality, nursing home admission, and disability.

т0

Name	Age	
Primary Goals (6 months)	Today's Date	
Primary Goals (1 year + )	Form completed by	

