### 6.2. Secondary endpoints

The secondary endpoints are:

- Checking hospital readmission at 60 and 90 days after hospital discharge to evaluate longer term rates.
- Checking how many times the participant possibly got re-hospitalized.
- Improving health status of older person in terms of general quality of life and physical performance. It
  will be accessed through EQ Visual Analogue Scale [26] and Short Form Health Survey 12 items [27] for
  general wellbeing status and Short Physical Performance Battery [23] for physical performance and
  functional status;
- Accessing the usability of the system, to be evaluated through the System Usability Scale [28] to check specific dashboard usability
- Supporting the empowerment of participants in terms of digital/eHealth literacy skills achievement, skills that will be assessed through eHeals scale [29].
- Evaluate acceptability, usability, effectiveness and willingness to pay of the system through semistructured interviews;
- Evaluation of clinical resource utilization through interviews.

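### SPPB gait item: the seconds bands for scores 1 and 2 overlap for walks above 5.7 s and up to 6.5 s on all four forms, and the 6.5 s limit contradicts the speeds printed beside it

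*Protocol*

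**What the plan says.** Section 6.2 names the "Short Physical Performance Battery [23] for physical performance and" functional status among the secondary endpoints, and section 3.2 lists it too. It is the only physical-performance measure there. Table 5 schedules it at R, T1, T2 and T3, but not at T0.

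The gait item ("6. 8' Walk (2.44 meters") tells the assessor to record the time "take to walk 8'. Then complete ordinal scoring". The scoring key for a completed walk is:

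- "1 = >5.7 sec (<0.43 m/sec")
- "2 = 4.1-6.5 sec (0.44-0.60" m/s)
- "3 = 3.2-4.0 (0.61-0.77 m/sec")
- "4 = <3.1 sec (>0.78 m/sec")

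A score of 0 is for those who could not do the walk. The item feeds a summary score: "Range: 0 (worst performance) to 12 (best performance"). The T1, T2 and T3 forms repeat the same limits.

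**The concern.** Two scores are available for one measured time. A walk of 6.0 s exceeds 5.7 s, so it scores 1. It also lies between 4.1 and 6.5 s, so it scores 2. The form gives no rule for choosing.

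Section 9 plans pre/post comparisons within groups and a repeated-measures ANOVA of change over time. If the choice differs between two visits or two raters, an unchanged walk shows up as a gain or loss of one point. A real improvement across the boundary can also be hidden. Assessments run at three sites with different staff, and eligibility reaches CFS 7 and includes people who walk with support, so walks near 0.4 m/s are plausible in this population.

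**Working it through.** **Inputs**, all from the gait item: course length 2.44 m and the printed limits in seconds and m/s.

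**Formula:** speed = 2.44 / time, and the reverse.

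**Step 1. Convert each printed time limit and compare it with the speed on its own line.**

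| Limit (s) | 2.44 / time (m/s) | Speed printed for that band | Agrees? |
|---|---|---|---|
| 3.1 (score 4) | 0.787 | above 0.78 | yes |
| 3.2 (score 3, fast end) | 0.763 | 0.61 to 0.77 | yes |
| 4.0 (score 3, slow end) | 0.610 | 0.61 to 0.77 | yes |
| 4.1 (score 2, fast end) | 0.595 | 0.44 to 0.60 | yes |
| 6.5 (score 2, slow end) | 0.375 | 0.44 to 0.60 | **no** |
| 5.7 (score 1) | 0.428 | below 0.43 | yes |

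Only 6.5 s fails. Taking 8 ft as 2.4384 m gives 0.3751 m/s at 6.5 s and changes nothing.

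**Step 2. Convert the speed limits at the score 1/2 boundary back to seconds.**

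- 2.44 / 0.44 = 5.55 s (slow end of score 2)
- 2.44 / 0.43 = 5.67 s (edge of score 1)

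The two speed limits and the 5.7 s limit all place the boundary at about 5.6 to 5.7 s. The 6.5 s figure stands alone against three others.

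**Step 3. Score every time on a 0.1 s grid.**

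- The eight values 5.8, 5.9, ..., 6.5 s meet both score 1 and score 2 by seconds. Their speeds run from 0.42 down to 0.38 m/s, so by speed all eight meet score 1 only.
- Exactly 5.7 s meets score 2 only by seconds, because score 1 requires more than 5.7 s. The ambiguous interval is therefore above 5.7 s and up to 6.5 s.
- Exactly 3.1 s has no score by seconds: score 4 is below 3.1 and score 3 starts at 3.2. By speed (0.787 m/s) it is a 4.

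**Step 4. Size.** The overlap is between adjacent scores, so one walk can move the item by at most 1 point, and the SPPB total by at most 1 of 12. For example, a participant who walks 6.0 s (0.407 m/s) at both R and T1, scored 2 and then 1, shows a one-point decline with no change in performance.

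**The case against.** The strongest reply is that the form resolves itself and the data are recoverable. The speed bands do not overlap, they put the whole disputed interval in score 1, and each form has a field for the raw time. This limits the harm: the slip can be identified, and scores can be recomputed where the time was entered. It does not cure the key, because assessors work in seconds and no text gives the speeds precedence.

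A reader might go further and infer that the overlap distorts the endpoint. The documents do not support that. They give no walk-time distribution, so the share of walks in the window is unknown. The sample is not uniformly frail either: CFS 2 to 7 is eligible, and section 7 classes scores 1 to 3 as non-frail.

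A reader might also infer bias between arms, on the ground that assessors who know the allocation could choose the score. That is speculative. Bias needs the rule to differ by arm, and nothing says it would. Section 8.2 describes the T1 SPPB for the experimental group only, and section 8.1 says controls are simply checked for re-hospitalization. On that text there is no T1 comparison of SPPB between arms to bias, and sections 8.3 and 8.4 are less clear for T2 and T3.

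Finally, it may seem enough to change 6.5 to 5.6 in the score 2 band. With score 1 left at more than 5.7 s, a walk of exactly 5.7 s would then have no score.

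**Conclusion.** The point stands as a scoring-key error in a named secondary endpoint. On all four SPPB forms, walks above 5.7 s and up to 6.5 s meet both score 1 and score 2, and 6.5 s is the faulty limit by the form's own speeds. The effect is at most 1 of 12 points for a walk in that window. It takes the form of misclassification and possible false one-point changes between visits or raters.

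The conclusion rests only on figures printed on the form and on the assumption that assessors score from seconds, as the instructions direct. The number of participants affected cannot be computed from the protocol. The primary endpoint and the sample size do not depend on this item.

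**What to change.** On all four forms, reconcile the seconds bands with the printed speeds and make them contiguous:

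- Let score 2 end where score 1 begins, at about 5.6 to 5.7 s; for example, 4.1 to 5.7 s against more than 5.7 s. State the edge explicitly, because 5.7 s is 0.428 m/s. That rounds to 0.43, which falls in neither printed speed band.
- Close the gap at 3.1 s, and state the precision to which times are recorded.
- Check the chair-stand item in the same pass: exactly 16.7 s and exactly 11.1 s have no score there.

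Derive the ordinal score from the recorded walk time by one stated rule, and recompute any scores already entered.

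The cost is a few limits on four forms and a short rescoring step. No new data are needed where the time field was completed.

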# A. How would you rate your abilities today in the following 9 areas when using your current AT or other support?

- For item 1-9, mark the best response (1 for Poor through 5 for Excellent)
- Under Name of Support write the name of the support you use where relevant (example: "eyeglasses" for #1, seeing)

Write a plus [+] in the spaces where you expect to need more support over the next year (example: "eyeglasses" gets [+] if you'll expect to need stronger lenses during the next year). Write a [-] in the spaces where you expect to need less support, and a [0] where you expect your support should stay the same over the next year.

	Poo	or	Averaş	ge.	Excellent	Name of Support	Need more[+], less [-], same [0]
1.Seeing	1	2	□3	□4	□ 5		
2.Hearing	1	□2	□3	□4	□ 5		
3.Speech	1	□2	□3	□4	□ 5		
4.Understanding, remembering	1	□2	□3	□4	5		
5.Physical strength/stamina	1	□2	□3	□4	□ 5		
6.Lower body use (hips, legs, feet)	1	□2	□3	□4	5		
7.Grasping and use of fingers	1	□2	□3	Π4			
8.Upper body (arms, shoulders, trunk)	1	□2	□3	Π4	□ 5		
9.Mobility (getting from place to place)	□ 1	□2	□3	Π4	□ 5		

### B. How satisfied are you currently in the following areas?

- For item 10 21, mark the best response (1 for Not satisfied through 5 for Very Satisfied)
- Which 3 items are most important to you? Under 3 Most Importnt, write #1, #2 or #3 for the three areas that concers you most (#1 = most important). Leave the other lines blank.
- For your 3 Most Important items, write the primary obstacles and barriers you face in the space beside that item

	No Satist	t fied	Satisfie	d S	Very atisfied	3 Most Important
10.Personal care and household activities	1	□2	□3	□4	□5	
11.Physical comfort & well-being		□2	□3	□4	□5	
12.Overall health		□2		□4	□5	
13.Freedom to go wherever desired		□2	□3	Π4	□5	
14.Participation in desired activities		□2	□3	Π4	□5	
15.Educational attainment	□ 1	2	□3	Π4	□5	
16.Employment status/potential		□2		□4	□5	
17.Family relationships	$\Box 1$	□2	□3	□4	□5	
18.Close, intimate relationships		□2	□3	□4	□5	
19.Autonomy and self-determination (choosing)	□ 1	□2	□3	Π4	□5	
20.Fitting in, belonging, feeling connected		□2	□3	□4	□5	
21. Emotional well-being		□2	□3	□4	□5	

C. Please mark all the statements below that describe you. Mark only those *frequently* or often apply to you and ignore those that very *rarely or never* apply to you.

22.I have the support I want from family

□23.I have the support I want from friends

□24.I feel encouraged by therapists, caregivers

□25. I feel the general public accepts me

□26.I aspire to go to school or work

□27.I have many things I want to accomplish

□28.I do what my therapists say without question

□29.I view my therapist(s) as friends, too

□ 30.I am often frustrated or overwhelmed

□ 31.I am curious & excited about new things

□ 32.I am determined to meet my goals

□ 33.I am usually calm and patient

□ 34.My life has purpose, meaning

□35.I am self-disciplined

□36.I am often angry

□ 37.I am often depressed

□38.I prefer to be left alone

39.I am often discouraged

□40.I am quite resourceful

□41.I like having a challenge

□42.I am responsible & reliable

□43. I am generally satisfied with my life

□44.I find technology interesting

□45.I am cooperative

46.I prefer a quiet lifestyle

□47.I often feel isolated & alone

□48.I accomplish what I set out to do

49.I am not sure who I am now

□ 50.I want more independence

□ 51.I have a good self image

52.1 often feel insecure

□ 53.I feel as if I have little privacy

□ 54.My therapist(s) know better than I what I need

## Assistive Technology Device Predisposition Assessment For Comparing Devices to Meet Desired Outcomes

Name	Age	
Primary Goals (6 months)	Today's Date	
Primary Goals (1 year + )		

**DIRECTIONS:** Write the name of each device you are considering in the boxes below under *Device*. An example has been provided. For each devide, enter a [x] for the 3 items (A-L) that are most important to you. Then rate each device on the 12 items (A-L) according to the following scale and write your ratings in the appropriate boxes:

5 = All the time (100% of the time)

- fram (around 75%) of the time)
- 2 = Sometimes (around 25% of the time)
- 4 = Often (around 75% of the time)
- 1 = Not at all (0% of the time)0 = Not applicable
- 3 = Half the time, neutral (about 50% of the time)

3 Q	Question	Example	Device 1:	Device 2:	Device 3:
		Quad			
		Cane	(device	(device	(device
			name)	name)	name)
Α	This device will help me to	5		a andrai a de	10
	achieve my goals (including				
	the primary AT goals written				
01.10	above)			8	
B	This device will benefit me	3			
	and impreve my quality of				
	life	100101-001			
С	I am confident I know how to	X 4	2		
	use this device and its various				
	features				
D	I will feel more secure (safe,	X 5	25. 2	5	
	sure of myself) when using				
	this device				

ermony			
This device will fit well with	4		
my accustomed routine			
I have the capabilities and	X 3		
stamina to use this device			
without discomfort, stress and			
fatigue		c	
The supports, assistance and	4		
accommodations exist for			
successful use of this device		8	
This device will physically fit	3		
in all desired environments			
(car, living room, etc.)			
I will feel comfortable (and	4		
not self-conscious) using this			
device around family			
I will feel comfortable (and	4	0	
not self-conscious) using this	101 s		
device around friends			
I will feel comfortable (and	4		
not self-conscious) using this			
device at school or work			
I will feel comfortable (and	4		
not self-conscious) using this			
device around the community			
Total (add A-L)	47		
	This device will fit well with my accustomed routine I have the capabilities and stamina to use this device without discomfort, stress and fatigue The supports, assistance and accommodations exist for successful use of this device This device will physically fit in all desired environments (car, living room, etc.) I will feel comfortable (and not self-conscious) using this device around family I will feel comfortable (and not self-conscious) using this device around friends I will feel comfortable (and not self-conscious) using this device at school or work I will feel comfortable (and not self-conscious) using this device at school or work I will feel comfortable (and not self-conscious) using this device at school or work I will feel comfortable (and not self-conscious) using this device around the community Total (add A-L)	This device will fit well with my accustomed routine4I have the capabilities and stamina to use this device without discomfort, stress and fatigueX 3The supports, assistance and accommodations exist for successful use of this device4This device will physically fit in all desired environments (car, living room, etc.)3I will feel comfortable (and not self-conscious) using this device around family4I will feel comfortable (and not self-conscious) using this device around friends4I will feel comfortable (and not self-conscious) using this device around friends4I will feel comfortable (and not self-conscious) using this device around friends4I will feel comfortable (and not self-conscious) using this device around friends4I will feel comfortable (and not self-conscious) using this device around friends4I will feel comfortable (and not self-conscious) using this device around the community4Total (add A-L)47	This device will fit well with my accustomed routine4I have the capabilities and stamina to use this device without discomfort, stress and fatigueX3The supports, assistance and accommodations exist for successful use of this device44This device will physically fit in all desired environments (car, living room, etc.)31I will feel comfortable (and not self-conscious) using this device around family44I will feel comfortable (and not self-conscious) using this device around friends44I will feel comfortable (and not self-conscious) using this device around friends44I will feel comfortable (and not self-conscious) using this device around friends44I will feel comfortable (and not self-conscious) using this device around friends44I will feel comfortable (and not self-conscious) using this device at school or work44I will feel comfortable (and not self-conscious) using this device at school or work44I will feel comfortable (and not self-conscious) using this device around the community4747
